6.3 Laboratory Test Abnormalities

The following laboratory abnormalities should be captured on the nonserious AE CRF Page or SAE Report Form (paper or electronic) as appropriate:

- Any laboratory test result that is clinically significant or meets the definition of an SAE

- Any laboratory abnormality that required the subject to have the study drug discontinued or interrupted
- Any laboratory abnormality that required the subject to receive specific corrective therapy.

It is expected that wherever possible, the clinical, rather than the laboratory term would be used by the reporting investigator (eg, anemia versus low hemoglobin value).

6.4 Pregnancy

If, following initiation of the investigational product, it is subsequently discovered that a study subject is pregnant or may have been pregnant at the time of investigational product exposure, including during at least 6 half lives after product administration, the investigational product will be permanently discontinued in an appropriate manner (eg, dose tapering if necessary for subject safety). Protocol-required procedures for study discontinuation and follow-up must be performed on the subject unless contraindicated by pregnancy (eg, x-ray studies). Other appropriate pregnancy follow-up procedures should be considered if indicated.

The investigator must immediately notify the BMS (or designee) Medical Monitor of this event and complete and forward a Pregnancy Surveillance Form to BMS (or designee) within 24 hours and in accordance with SAE reporting procedures described in [Section 6.1.1](#).

Follow-up information regarding the course of the pregnancy, including perinatal and neonatal outcome and, where applicable, offspring information must be reported on the Pregnancy Surveillance Form.

Any pregnancy that occurs in a female partner of a male study participant should be reported to the sponsor. Information on this pregnancy will be collected on the Pregnancy Surveillance Form.

6.5 Overdose

An overdose is defined as the accidental or intentional administration of any dose of a product that is considered both excessive and medically important. All occurrences of overdose must be reported as an SAE (see Section 6.1.1 for reporting details.).

6.6 Potential Drug Induced Liver Injury (DILI)

Wherever possible, timely confirmation of initial liver-related laboratory abnormalities should occur prior to the reporting of a potential DILI event. All occurrences of potential DILIs, meeting the defined criteria, must be reported as SAEs (see Section 6.1.1 for reporting details).

Potential drug induced liver injury is defined as

1. AT (ALT or AST) elevation > 3 times upper limit of normal (ULN)

AND

2. Total bilirubin > 2 times ULN, without initial findings of cholestasis (elevated serum alkaline phosphatase),

AND

3. No other immediately apparent possible causes of AT elevation and hyperbilirubinemia, including, but not limited to, viral hepatitis, pre-existing chronic or acute liver disease, or the administration of other drug(s) known to be hepatotoxic.

6.7 Other Safety Considerations

Any significant worsening noted during interim or final physical examinations, electrocardiograms, x-rays, and any other potential safety assessments, whether or not these procedures are required by the protocol, should also be recorded as a nonserious or serious AE, as appropriate, and reported accordingly.

7 DATA MONITORING COMMITTEE AND OTHER EXTERNAL COMMITTEES

7.1 Data Monitoring Committee

Not Applicable.

7.2 Independent Central Adjudication Committee

The Independent Central Adjudication Committee (ICAC) will be responsible for validating outcome events as specified in the protocol and according to guidelines using standardized criteria.

The ICAC reviews and adjudicates all suspected symptomatic DVT, PE, major bleeds, clinically relevant non-major bleeds, minor bleeds, thrombocytopenia and causes of death.

8 STATISTICAL CONSIDERATIONS

8.1 Sample Size Determination

The sample size of the study is determined by requirement of regulatory agency rather than statistical considerations. With 500 subjects in the apixaban arm and event rate of 4.36% for ISTH major or clinically relevant non-major bleeding, the width of the 95% CI for the event rate will be (2.6%, 6.2%) and width of the CI is 3.6%.

8.2 Populations for Analyses

The term “treatment period” refers to the period between the first administration of study medication (post-surgery oral apixaban) and two days after the last administration of study medication (end of treatment). The “treatment period” will be the basis for the summaries of

safety and efficacy. Summaries of safety and efficacy data will include all subjects receiving any study medication.

8.3 Endpoint Definitions

Primary Endpoint:

The primary study endpoint is a composite of International Society on Thrombosis and Haemostasis (ISTH) major bleeding/clinically relevant non-major bleeding (CRNM) in subjects undergoing elective total knee or hip replacement at the end of treatment + 2 days, where ISTH major bleeding is

- Fatal or
- Bleeding in a critical organ, such as brain, spine, eye, retroperitoneum, joint, heart sac, or skeletal muscle (and resulting in compartment syndrome), or
- Bleeding that results in a fall of hemoglobin of 2 g/dL or more or transfusion of 2 units or more of packed red cells or whole blood within 24 hours

and CRNM bleeding is bleeding that

- Is clinically acute and overt
- Does not satisfy criteria as a major bleed but requires medical intervention, such as a visit to a physician's office, emergency room, or urgent care center for epistaxis.

Secondary Endpoints:

The secondary endpoint will be: The composite of VTE/all cause death at the end of treatment + 2 days, where VTE is the combination of deep vein thrombosis and non-fatal pulmonary embolism.

8.4 Analyses

8.4.1 Demographics and Baseline Characteristics

Frequency distribution and summary statistics for demographic and baseline variables will be presented by treatment group and for all subjects combined. Key demographic and baseline variables to be summarized include: age, gender, race, vital signs (systolic blood pressure, diastolic blood, pressure, and heart rate), medical history, knee or hip replacement surgery experience, intra-operative details, and post-surgical patient care characteristics. The summary will be presented for all subjects.

8.4.2 Efficacy Analyses

The event rates and their 95% confidence intervals of composite of venous thromboembolism (VTE) and all cause death during the treatment period will be summarized. Subgroup analyses by surgery type will also be conducted.

8.4.3 Safety Analyses

Bleeding is the primary safety outcome measure. The event rate of adjudicated major bleeding or clinically relevant non-major bleeding events during the treatment period will be summarized. Subgroup analyses by surgery type will also be conducted.

An additional analysis will summarize all adjudicated major bleeding or clinically relevant non-major bleeding occurring during the treatment period, which begins with the first dose of study medication.

In addition, an analysis of major or clinically relevant non-major bleeding events will look at the bleeding events that occur prior to the administration of apixaban. Additional details will be provided in the Statistical Analysis Plan.

The incidence of adverse events and of marked abnormalities in clinical laboratory tests will be summarized by treatment group for both the treatment and follow-up period.

All adverse events that are serious or that result in discontinuation of study therapy will be described in depth. K-M estimator will be used to estimate the rate of early discontinuation due to any reason.

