- Subject has specific elevated liver function test (LFTs) results
- Subject has a severe adverse event that may require the use of anticoagulants, antiplatelet agents, thrombin inhibitors, glycoprotein IIB/IIIa antagonists or other thrombotic agents
- Subject has an increased risk of bleeding complications eg persistent bleeding after surgery or difficult (more than 2 failed attempts) or traumatic (bloody spinal fluid) lumbar puncture.

All subjects who discontinue should comply with protocol specified follow-up procedures as outlined in [Section 5](#). The only exception to this requirement is when a subject withdraws consent for all study procedures or loses the ability to consent freely (ie, is imprisoned or involuntarily incarcerated for the treatment of either a psychiatric or physical illness).

If a subject was withdrawn before completing the study, the reason for withdrawal must be entered on the appropriate case report form (CRF) page.

All subjects who discontinue study medication prematurely and have received at least one dose of post-surgical oral study medication should be encouraged to return for an in person visit on Day 7, Day 12 (TKR) or Day 35 (THR) and follow up visit at Day 42 (TKR) or Day 65 (THR). Alternatively those visits would be performed by phone.

Subjects who require a revision of their hip or knee replacement during the study's treatment period should have their apixaban stopped at least 48 hours before their revision surgery.

Patients who withdraw consent for treatment with study drug should still receive follow-up for adverse events and outcomes unless they withdraw consent for follow-up as well.

If a subject is lost to follow-up, every effort should be made to contact the subject and perform these procedures. At minimum the vital status should be collected.

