## 6 STUDY PERIODS, TREATMENT REGIMENS AND POPULATIONS FOR ANALYSES

### 6.1 Study Periods

In all listings, summaries and statistical analyses, the term '**Intended Treatment Period**' refers to the period that starts with the enrollment.

In all listings, summaries and statistical analyses, the term '**Treatment Period**' will refer to the period between the first administration of study medication (post-surgery oral apixaban) and 2 days after the last administration of study medication (end of treatment). This period will be the basis for the summaries of safety and efficacy.

In all listings, summaries and statistical analyses, the term "**Follow-up Period**" will refer to the period starting after the "Treatment Period" ended through 30 days after discontinuation of study drug (for treated subjects).

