### 6.2 Treatment Regimens

Safety and efficacy outcomes will be summarized according to the **Treated** group, which subjects who received at least one dose of study drug.

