## 7.6 Safety

Bleeding is the primary safety outcome measure. The event rate of adjudicated major bleeding or clinically relevant non-major bleeding events during the treatment period will be summarized. Subgroup summary for bleeding by surgery type (knee or hip) will also be conducted.

The incidence of adverse events will be summarized for both the treatment and follow-up period by surgery type (knee or hip). Any post-dose marked abnormalities in clinical laboratory tests will be listed.

All adverse events that are serious or that result in discontinuation of study therapy will be described in depth.

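### The SAP does not specify the protocol's analysis of bleeding before the first apixaban dose, and the dosed-only rule in both documents would leave never-dosed bleeders out of it

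*Protocol*

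**What the plan says.** Protocol 8.4.3 plans the treatment-period bleeding summary and, separately, a pre-dose one: "an analysis of major or clinically relevant non-major bleeding events will look at the bleeding events that occur prior to the administration of apixaban". It adds: "Additional details will be provided in the Statistical Analysis Plan".

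SAP 7.6 covers the first only: "The event rate of adjudicated major bleeding or clinically relevant non-major bleeding events during the treatment period will be summarized". SAP 6.1 defines that period as "the period between the first administration of study medication (post-surgery oral apixaban) and 2 days after the last administration of study medication". SAP 6.1 also defines an Intended Treatment Period that "refers to the period that starts with the enrollment", but gives it no end, and no analysis in the supplied text uses it.

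The population rule is the same in both documents. Protocol 8.2: "Summaries of safety and efficacy data will include all subjects receiving any study medication". SAP 6.2: "Safety and efficacy outcomes will be summarized according to the Treated group, which subjects who received at least one dose of study drug". SAP 6.3 defines an Enrolled Population as everyone who signed consent, but no outcome analysis in the SAP text uses it.

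The SAP's document history for version 2.0 lists two changes, removal of the evaluable population and a new compliance formula. Neither concerns pre-dose bleeding.

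**The concern.** Bleeding is the primary endpoint, and Amendment 01 removed the enoxaparin arm. The protocol separates bleeding before apixaban from bleeding on it, which helps a reader interpret a single-arm rate in surgical patients. Followed as written, the supplied SAP produces only the on-drug part.

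Restoring the protocol's sentence would not be enough. Some subjects may be enrolled, have surgery, bleed and never receive apixaban. They are the ones a pre-dose tally most needs to count, and the dosed-only rule removes them. The dosed population may then be partly selected on good haemostasis after surgery, with no planned bleeding table to show how strongly.

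**Working it through.** **1. Is the analysis anywhere in the SAP?** Each place where it could appear:
- SAP 4.1 (primary endpoint): end of treatment + 2 days.
- SAP 6.1: the treatment period opens at first dose; the Intended Treatment Period is defined but unused.
- SAP 7.6: treatment-period bleeding, adverse events in the treatment and follow-up periods, and descriptions of serious events. No pre-dose bleeding.
- SAP 7.1, 7.6.1 and 7.6.3: pointers to a Core SAP that was not supplied. None mentions pre-dose bleeding.

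**2. Can never-dosed bleeders exist?** Yes.
- Protocol 3.1.2: enrollment may occur from 4 days before surgery to 24 hours after it.
- Protocol 3.1.3: the first dose comes 12 to 24 hours after wound closure.
- Protocol 3.4.2 lists among the reasons to discontinue: "Subject has an increased risk of bleeding complications eg persistent bleeding after surgery".
- Protocol 3.4.2 addresses its return-visit instruction to discontinuing subjects with at least one dose, which implies that some may have none.

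**3. Direction of the bias.** Let N subjects be assigned and operated, d bleed before dosing and are never dosed, m are undosed without bleeding, and x bleed before dosing but are dosed later. The dosed-only pre-dose rate is x/(N − d − m); the full rate is (x + d)/N. The dosed-only rate is lower whenever d/(d + m) > (x + d)/N, that is, whenever bleeding is more common among the never-dosed than overall. That is to be expected if bleeding is a reason for not dosing.

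**4. The plan's own figure.** Inputs from SAP 5: 500 subjects, planning rate 4.36%. A Wald interval with 22/500 = 4.4% gives 0.044 ± 1.96 × √(0.044 × 0.956/500) = 2.60% to 6.20%, width 3.60%, as stated. This point does not affect that interval.

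**5. Illustrative size.** The documents give neither the number never dosed nor a pre-dose bleeding rate. Assume 500 assigned and operated, d never-dosed bleeders, everyone else dosed, and 4.36% of the dosed bleeding on treatment. The rate from surgery onward, leaving out any pre-dose bleeds in subjects later dosed, is [(500 − d) × 0.0436 + d]/500:

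| d (assumed) | From-surgery rate |
|---|---|
| 0 | 21.8/500 = 4.36% |
| 5 | (21.58 + 5)/500 = 5.3% |
| 10 | (21.36 + 10)/500 = 6.3% |
| 25 | (20.71 + 25)/500 = 9.1% |

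Each such subject adds (1 − 0.0436)/500 = 0.19 percentage points. With whole events, the treated-only rate barely moves: 22/495 = 4.44%, 21/490 = 4.29% and 21/475 = 4.42% for d = 5, 10 and 25. The planned primary table therefore cannot show whether d is small or large.

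These figures are not lower bounds. With d = 5 and another 25 undosed without bleeding, the result is (470 × 0.0436 + 5)/500 = 5.1%, below 5.3%.

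**6. Would the data exist?** Three places in the protocol disagree.
- 6.2.1 starts nonserious adverse event collection at the start of study drug.
- Tables 5.1-1 and 5.1-2 schedule AE/SAE assessment from enrollment and on the day of surgery.
- 5.3 has bleeding assessed at every post-surgery visit.

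Serious events are covered from consent (6.1.1). Nonserious CRNM bleeds before dosing may not be recorded consistently.

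**The case against.** The Core SAP may contain the analysis, and the Intended Treatment Period may be used there. That cannot be ruled out, so the finding is limited to the supplied SAP. But the protocol assigns the details to the SAP, and this SAP has no pointer for them. Serious pre-dose bleeds might still be described individually under SAP 7.6, although SAP 6.2 makes that uncertain, and descriptions give no rate.

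The size is assumed. It also adds a surgical-window count to an on-treatment rate, which makes it a different quantity from the primary endpoint and not a correction of it. This stands: 4.36% is a planning figure, and the table above shows sensitivity only.

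The selection mechanism is partly inferred. Protocol 3.4.2 lists persistent bleeding under discontinuation and does not say that such subjects are never dosed. Protocol 4.2 puts assignment before surgery, whereas 3.1.2 allows enrollment up to 24 hours after it. This also stands: such subjects are possible, but their number cannot be judged.

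A reader might infer that the SAP introduced the dosed-only restriction. It did not; Protocol 8.2 already has it. A reader might also infer that pre-dose bleeding is the study's only internal reference. Neither document gives it that role. A window of surgery plus 12 to 24 hours is not comparable with 12 or 35 days on drug, and off-drug adverse events in follow-up are still summarized.

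**Conclusion.** The concern holds in this form: the supplied SAP leaves unspecified, without explanation, an analysis of the primary safety outcome that the protocol planned and assigned to it. The dosed-only rule in both documents would remove never-dosed bleeders even if the analysis were run. The expected direction is an understatement of pre-dose bleeding, provided bleeding is more common among never-dosed subjects than overall. The size is unknown: about 0.2 percentage points of a from-surgery rate per such subject, if 500 are assigned and all others are dosed.

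It does not follow that the primary rate is wrong. The treated population and treatment period suit an on-treatment bleeding rate and should stay. The gap should be closed, but it does not invalidate the study.

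**What to change.** - **Add one descriptive table to SAP 7.6**: adjudicated major or CRNM bleeding from surgery to first dose, by surgery type, in all subjects assigned to apixaban through IVRS who had surgery, whether or not dosed. For never-dosed subjects, state where the window ends. Show the number never dosed because of bleeding.
- **Name the population explicitly.** The SAP's Enrolled Population is everyone who signed consent and is not the right denominator.
- **Exempt this table** from the dosed-only rule in Protocol 8.2 and SAP 6.2. Leave the primary analysis unchanged.
- **Reconcile Protocol 6.2.1** with Tables 5.1-1 and 5.1-2 and with 5.3, so that nonserious pre-dose CRNM bleeds are recorded and sent for adjudication. Protocol 7.2 already covers suspected major and CRNM bleeds without a dosing condition.
- If the sponsor no longer wants the analysis, document its removal and the reason.

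The cost is SAP wording, one table, a data-collection clarification in the protocol and a few more events to adjudicate. Undercounting remains possible: hemoglobin is scheduled only at screening, enrollment and hospital discharge, so a pre-dose 24-hour fall is not measured systematically. Subjects whose bleeding prevented assignment after surgery would also not be counted. The table should state both limits.

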8.4.4 Other Analyses

Not Applicable.

8.5 Interim Analyses

Not Applicable.

9 STUDY MANAGEMENT

9.1 Compliance

9.1.1 Compliance with the Protocol and Protocol Revisions

The study shall be conducted as described in this approved protocol. All revisions to the protocol must be discussed with, and be prepared by, BMS. The investigator should not implement any deviation or change to the protocol without prior review and documented approval/favorable opinion from the IRB/IEC of an amendment, except where necessary to eliminate an immediate hazard(s) to study subjects.

If a deviation or change to a protocol is implemented to eliminate an immediate hazard(s) prior to obtaining IRB/IEC approval/favorable opinion, as soon as possible the deviation or change will be submitted to:

- IRB/IEC for review and approval/favorable opinion
- Bristol-Myers Squibb
- Regulatory Authority(ies), if required by local regulations

Documentation of approval signed by the chairperson or designee of the IRB(s)/IEC(s) must be sent to BMS.

If an amendment substantially alters the study design or increases the potential risk to the subject: (1) the consent form must be revised and submitted to the IRB(s)/IEC(s) for review and approval/favorable opinion; (2) the revised form must be used to obtain consent from subjects currently enrolled in the study if they are affected by the amendment; and (3) the new form must be used to obtain consent from new subjects prior to enrollment.

If the revision is an administrative letter, investigators must inform their IRB(s)/IEC(s).

9.1.2 Monitoring

Representatives of BMS must be allowed to visit all study site locations periodically to assess the data quality and study integrity. On site they will review study records and directly compare them with source documents, discuss the conduct of the study with the investigator, and verify that the facilities remain acceptable.

In addition, the study may be evaluated by BMS internal auditors and government inspectors who must be allowed access to CRFs, source documents, other study files, and study facilities. BMS audit reports will be kept confidential.

The investigator must notify BMS promptly of any inspections scheduled by regulatory authorities, and promptly forward copies of inspection reports to BMS.

9.1.3 Investigational Site Training

Bristol-Myers Squibb will provide quality investigational staff training prior to study initiation. Training topics will include but are not limited to: GCP, AE reporting, study details and procedure, electronic CRFs, study documentation, informed consent, and enrollment of WOCBP.

9.2 Records

9.2.1 Records Retention

The investigator must retain all study records and source documents for the maximum period required by applicable regulations and guidelines, or institution procedures, or for the period specified by the sponsor, whichever is longer. The investigator must contact BMS prior to destroying any records associated with the study.

BMS will notify the investigator when the study records are no longer needed.

If the investigator withdraws from the study (eg, relocation, retirement), the records shall be transferred to a mutually agreed upon designee (eg, another investigator, IRB). Notice of such transfer will be given in writing to BMS.

9.2.2 Study Drug Records

It is the responsibility of the investigator to ensure that a current disposition record of investigational product (those supplied by the sponsor) is maintained at each study site where study drug is inventoried and dispensed. Records or logs must comply with applicable regulations and guidelines and should include:

- amount received and placed in storage area
- amount currently in storage area

- label ID number or batch number
- amount dispensed to and returned by each subject, including unique subject identifiers
- amount transferred to another area/site for dispensing or storage
- non-study disposition (eg, lost, wasted)
- amount destroyed at study site, if applicable
- amount returned to the sponsor
- retain samples for bioavailability/bioequivalence, if applicable
- dates and initials of person responsible for Investigational Product (IP) dispensing/accountability, as per the Delegation of Authority Form.

BMS will provide forms to facilitate inventory control if the investigational site does not have an established system that meets these requirements.

